7.2.4 Other Efficacy

Not applicable in this study.

7.2.5 Quality of Life Assessments

Not applicable in this study.

7.2.6 Exploratory endpoint

7.3 Safety Assessments

7.3.1 Adverse Events

Summaries

All AEs for each subject, including multiple occurrences of the same event, will be presented in full in a comprehensive listing including subject number, treatment, severity, seriousness, action taken, outcome, relationship to treatment, onset/stop date and duration.

AEs which start on or after dosing that are expressed or exacerbated are defined as treatment emergent adverse events (TEAEs).

The frequency and incidence of TEAEs will be summarized by System Organ Class (SOC) and Preferred Term (PT). The summary will be sorted by International Agreed Order (IAO) for SOC and alphabetical order for PT (or by frequency from the highest to the lowest).

Proportion of subjects with any TEAE, subjects with any related TEAE, subjects with any serious TEAE, and subjects with any TEAE leading to discontinuation of the study will be summarized.

Following summaries of TEAEs will be presented:

- Summary of AEs by SOC and PT
- Summary of related AEs by SOC, PT

For summaries of AEs multiple occurrences of the same event within a subject will be counted once in the summaries by SOC and PT; multiple occurrences of the same event within a subject will be counted once in the maximum intensity category (severe > moderate > mild) and/or maximum drug relationship category (reasonable possibility > no reasonable possibility). If intensity or relationship is found to be missing the most severe occurrence will be imputed for that particular summary.

7.3.2 Laboratory Tests

Laboratory parameter values and changes from baseline, except for urinalysis will be summarized descriptively by analysis visit.

Clinical significance of laboratory findings will be evaluated by the Investigator with respect to pre-defined clinically relevant ranges taking into account the Investigator site's normal ranges. The laboratory data will be listed in full with clinically relevant values flagged (L=Lower than normal range, H=Higher than normal range or A=Abnormal if no reference range). A listing of laboratory values will be provided for subjects with any clinical significant findings (list relevant laboratory parameters only).

Lab parameter values and changes from baseline will be summarized descriptively by treatment group and analysis visit.

Shift tables will present the changes in clinically relevant categories from baseline to each analysis visit. The categories will be qualitative values for Urinalysis.

The test parameters(from central laboratory) are listed below.

- * Hematology tests: White blood cell count (WBC), red blood cell count (RBC), hematocrit (Ht), hemoglobin (Hb), platelets (Plt)
- * Blood biochemistry tests: AST (GOT), ALT (GPT), LDH, ALP, γ -GTP, total bilirubin (T-Bil), direct bilirubin (D-Bil), total cholesterol (T-Cho), triglycerides (TG), total protein (TP), CK (CPK), blood urea nitrogen (BUN), serum creatinine (Cre), eGFR, uric acid (UA), Na, K, Cl, albumin, glucose
- * Urinalysis (qualitative): Glucose, protein, occult blood

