j) Only white blood cell count (WBC), red blood cell count (RBC), hemoglobin (Hb), hematocrit (Ht), platelets (Plt), AST (GOT), ALT (GPT), LDH, ALP, γ -GTP, total bilirubin (T-Bil), CK (CPK), urea nitrogen (BUN), serum creatinine (Cre), and eGFR will be examined urgently in the hospital to confirm the eligibility as a case.

k) Only red blood cell (RBC), platelet (Plt), AST (GOT), ALT (GPT), LDH, ALP, total bilirubin (T-Bil), CK (CPK), urea nitrogen (BUN), and serum creatinine (Cre) will be measured in the hospital every day for 5 days from the start day of treatment to confirm the safety of subjects.

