9.2.4 Items Related to Safety Evaluation

9.2.4.1 Objective findings

(1) General laboratory tests: Hematology, serum chemistry, urinalysis

[Items to be measured from visit to before the start of administration]

The Investigator (or Subinvestigator) will perform emergency tests of the underlined items below in the hospital, confirm the eligibility as a subject, and record the date and time of blood sampling, date of confirmation of test results, and results of confirmation of test results (clinical significance) in the source documents. The date and time of blood sampling and test results will be recorded in the case report form.

In addition, all of the following tests will be measured at the contract laboratory testing institution, and the date of confirmation of the test results and the confirmation results (clinical significance) will be recorded. The test results provided by the contract laboratory testing institution will be retained by the study site and the sponsor.

The test items are as follows.

- Hematology: White blood cell count (WBC), Red blood cell count (RBC), Hematocrit (Ht), Hemoglobin (Hb), Platelets (Plt)
- Blood biochemistry: AST (GOT), ALT (GPT), LDH, ALP, γ -GTP, Total bilirubin (T-Bil), direct bilirubin (D-Bil), Total cholesterol (T-Cho), triglycerides (TG), total protein (TP), CK (CPK), Blood urea nitrogen (BUN), Serum creatinine (Cre), eGFR, Uric acid (UA), Na, K, Cl, albumin, glucose
- Urinalysis (qualitative): Sugar, protein, occult blood

[Items to be measured from the start of administration to the end of observation (3 months later)]

The Investigator (or Subinvestigator) must measure the underlined items below in the routine test in the hospital, confirm the test results, and record the date and time of blood sampling, date of confirmation of test results, and results of confirmation of test results (clinical significance) in the

source documents every day from Day1 (after the start of treatment) to Day5. The date and time of blood sampling and test results will be recorded in the case report form.

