11.2 Significant Adverse Events

For the purpose of examining the safety profile, AEs of special interest are defined as follows.

- (1) Renal disorder
Serum creatinine >2.0 mg/dL
- (2) Drug-induced liver injury
¹⁹ if all of the following definitions of Hy's law are met:
 - a) AST or ALT $> 3 \times$ ULN
 - b) Total bilirubin > 2 times the upper limit of normal
 - c) ALP $< 2 \times$ ULN
 - d) There is no explanation for the above laboratory abnormalities a), b), and c) other than investigational product.
- (3) Neurological disorders (medically significant changes on neurological examination in the healthy side)

If such an adverse event occurs, the investigator must inform the monitor immediately about the situation. The monitor will confirm with the investigator (subinvestigator) whether or not the study can be continued.

For significant adverse events, the sponsor will appropriately evaluate the occurrence status and frequency, and examine the appropriateness of study continuation and the necessity of protocol amendment.

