- d) Twice a day, at morning and at night, for 14 days. As a rule, the drug is administered for 14 days. However, in the period after the treatment has been administered for 7 days following treatment initiation and the NIHSS assessments have been completed, treatment may be stopped only if the (sub)investigator determines that the neurological symptoms associated with the primary disease have returned to their baseline levels, the patient's condition has stabilized, and that consequently continuing to administer the study drug would not be clinically meaningful, and administering the drug would only be detrimental for the subject in that it would restrict the

subject's freedom. (the subject may not be discharged).

- e) The mRS assessments will be performed using the Japanese-language version of the mRS questionnaire (Cerebrovasc Dis 2006;21:271-278) (Attachment 2: mRS Questionnaire; Attachment 3: mRS Assessment Criteria).
- f) The mRS assessment will also be performed prior to treatment initiation.
- g) Imaging will be performed after the end of the 72-hour continuous infusion (+ 2 days).
- h) The neurological assessments will be performed once in the period between the time of consent acquisition and Day 5.
- i) The standard 12-lead ECG, vital signs, and clinical laboratory tests (centralized measurements) will be performed before the end of the 72-hour continuous infusion (-1 day).
- j) The following tests will be conducted urgently at the hospital to confirm the patient's eligibility: WBC, RBC, hematocrit, hemoglobin, platelets, AST (GOT), ALT (GPT), LDH, ALP, γ -GTP, total bilirubin (T-Bil), CK (CPK), urea nitrogen (BUN), serum creatinine (Cre), and eGFR.
- k) The red blood cell (RBC), platelet (Plt), AST (GOT), ALT (GPT), LDH, ALP, total bilirubin (T-Bil), CK (CPK), urea nitrogen (BUN), and serum creatinine (Cre) levels only will be performed at the site every day from the day after treatment initiation through Day 5 after treatment initiation to confirm subject safety.

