6. GENERAL CONSIDERATIONS

Efficacy endpoints will be analysed on the FAS population and listed on the FAS population. Subjects will be analysed according to the treatment group they were randomised to. Safety analyses will be performed on the SAF. Subjects will be analysed according to the treatment group they were actually received.

In general, continuous variables will be summarized descriptively using the number of observations (n), mean, standard deviation (SD), median, minimum and maximum. Categorical variables will be summarized using frequency counts and percentages. The denominator for the percentages will be the total number of subjects in the relevant group and population (analysis set) being presented, unless otherwise specified (e.g., on some occasions, percentages maybe calculated out of the total number of subjects with available data at a particular visit and/or time point).

For each section, baseline is the last valid assessment prior to the start of IMP administration. For numerical variables, change from baseline will be calculated as the post-baseline value minus the baseline value. If baseline value cannot be determined for a particular variable, change from baseline will not be calculated.

Data will be handled as follows.

(1) Definition of missing data

When test values are missing, or could not be measured because of, for example, a problem with the test sample, these values will be handled as missing. In addition, no imputation will be made in case of missing values.

(2) Handling of the data at measurement time points

When summarizing the data at each measurement time point, data within the analysis time windows defined in Appendix 1 will be used. If multiple values were obtained within the time window, then the value closest to the planned assessment day will be used.

Unscheduled visits will not be displayed in by-visit summary tables, but will be included in the data listings.

Listings will include scheduled, unscheduled, retest and early discontinuation data.

The date and times of start and end of IMP administration will be taken from the Electronic Case Report Form (eCRF) Dosing form.

All medical history and adverse events will be coded from the actual term using the Medical Dictionary for Regulatory Activities (MedDRA) version 20.0.

All prior and concomitant medications will be coded using the World Health Organization (WHO) drug dictionary (Version: WHO DDE B2 Mar_2017).

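### The local Day 1–5 laboratory tests have no planned summary, and no listed table counts the renal and hepatic criteria of protocol 11.2

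*SAP*

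**What the plan says.** **What is measured.** Footnote k of protocol 9.1 says that ten analytes, among them creatinine, AST, ALT, ALP and total bilirubin, "will be measured in the hospital every day for 5 days from the start day of treatment to confirm the safety of subjects". Protocol 9.2.4.1 adds, for these site tests, that "The date and time of blood sampling and test results will be recorded in the case report form". The same section schedules central samples after the start of dosing on Days 4, 7, 10 and 14, at Week 3 and at discharge. Footnote k of SAP 3.2 gives a different start for the site tests: "every day from the day after treatment initiation through Day 5 after treatment initiation to confirm subject safety".

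**What the protocol singles out.** Section 11.2 defines three events of special interest: creatinine above 2.0 mg/dL, the Hy's law combination, and neurological disorders. It then states: "For significant adverse events, the sponsor will appropriately evaluate the occurrence status and frequency", and goes on to whether the study should continue and whether the protocol needs amending.

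**What the SAP plans.** Section 7.3.2 says "Lab parameter values and changes from baseline will be summarized descriptively by treatment group and analysis visit" and "The laboratory data will be listed in full with clinically relevant values flagged". Its list of analytes opens with "The test parameters(from central laboratory) are listed below". Section 6 adds that "Unscheduled visits will not be displayed in by-visit summary tables", with such values going to listings instead. The safety tables in section 14.2 cover adverse events, central-type laboratory summaries and shift tables, vital signs and ECG. The SAP does not mention the section 11.2 events.

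**The concern.** The trial compares two infusion regimens with the approved regimen, and the difference in exposure is concentrated in the first days. From protocol 8.3, the 72-hour totals are 0.16 + 0.4 × 72 = 28.96 mg/kg in group H and 0.08 + 0.2 × 72 = 14.48 mg/kg in group L. Six control doses of 30 mg come to 180 mg. At assumed body weights of 50 to 80 kg, group H receives about 1,448 to 2,317 mg, or 8 to 13 times the control amount. Renal and hepatic injury are two of the three events that the protocol names for special attention, and the daily site tests are the densest data on them in that period.

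If the SAP is followed exactly, those site values are not summarised, and nobody counts how many subjects in each arm crossed the protocol's own limits. A short-lived crossing that the investigator did not report as an adverse event would appear in no table. There is no data monitoring board (SAP 4.1), so the final tables carry more of the weight.

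**Working it through.** **1. Can the criteria be applied to the local data?** Section 11.2 needs creatinine for the renal criterion, and AST or ALT, total bilirubin and ALP for Hy's law items a to c. All five analytes are among the ten measured daily at the site, and the results are in the case report form. So the answer is yes, provided that site upper limits of normal are available for the multiples. Item d (no other explanation) cannot be read from laboratory values.

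**2. How do the two schedules overlap?**

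| Source | Local test days | Central draw in Days 1–5 | Local days with no central draw |
|---|---|---|---|
| Protocol 9.1 and 9.2.4.1 | 1, 2, 3, 4, 5 | Day 4 | 4 of 5 |
| SAP 3.2, footnote k | 2, 3, 4, 5 | Day 4 | 3 of 4 |

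**3. What do the planned outputs count?** In SAP 14.2, no table applies the creatinine limit or the Hy's law limits. In SAP 14.1 there is no laboratory listing, although 7.3.2 promises one. By contrast, SAP 7.3.4 sets five QTcF cut-offs and table 14.3.4.2 reports them, although section 11.2 does not name QTcF.

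**4. Was the omission declared?** Protocol 13.3.3 promises summary statistics for each laboratory parameter by group and time point, and does not limit this to central results. SAP section 8 declares two changes only: no per-protocol set and no formal efficacy tests. SAP section 10, on data not summarised, reads as not applicable.

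**5. Illustration of what central sampling would catch.** Assume that a rise starts on day s = 1, …, 5 with equal chance, lasts k days (s to s + k − 1), and is caught if that span includes a central draw on Day 4 or Day 7.

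- k = 1: s = 4, so 1/5 = 20%
- k = 2: s = 3, 4, so 2/5 = 40%
- k = 3: s = 2, 3, 4, 5, so 4/5 = 80%
- k = 4: s = 1, 2, 3, 4, 5, so 5/5 = 100%

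Daily local sampling on Days 1–5 catches all of these. With local sampling on Days 2–5 only, a one-day rise on Day 1 is missed locally too.

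SAP Appendix 1 lets the Day 4 laboratory draw fall on Day 3 or 4 and the Day 7 draw on Days 6 to 8. Repeating the count over these combinations gives:

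- k = 1: always 1/5, or 20%.
- k = 2: 2/5, or 3/5 if the second draw is on Day 6; 40% to 60%.
- k = 3: from 3/5 (second draw on Day 8) to 5/5 (draws on Days 3 and 6); 60% to 100%.
- k = 4: 5/5 except 4/5 with draws on Days 3 and 8; 80% to 100%.

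**The case against.** The strongest reply is that other routes exist. Under protocol 9.2.4.1 the investigator reviews every local result. Under 9.2.4.2 any clinically significant abnormality becomes an adverse event, whichever laboratory measured it. Section 11.2 itself frames its limits as adverse events. Adverse events and adverse reactions are tabulated by system organ class and preferred term, and SAP section 13 presents summaries by treatment group. A change that lasts until a central draw also enters the central summaries and shift tables. All of this stands, so a reader who infers that an early signal cannot appear by arm goes too far. The routes are still incomplete. Entry depends on the investigator's judgement, a test abnormality need not be reported when the related symptom already is, and preferred terms do not group subjects by the section 11.2 criteria.

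Three further inferences are tempting and are not supported:

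- *That section 11.2 promises a final table by arm.* It speaks of frequency but not of arms, and the rest of its sentence reads partly as surveillance during the trial. Protocol 13.3.3 promises no special-interest table either.
- *That most of the relevant data go unused.* Six central time points after the start of dosing measure the same analytes, against five local ones.
- *That the daily tests were placed to cover the infusion.* The stated purpose is subject safety, and Day 5 falls after a 72-hour infusion begun on Day 1.

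The rule on unscheduled visits is a side issue, because the daily tests are scheduled. It matters only for repeat tests, which the proposed count should include.

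Finally, recruitment stopped early and the SAP calls its results exploratory. That explains the loss of formal efficacy tests but not a gap in descriptive safety tables. SAP section 14 calls its list a minimum, so the tables may be added; it also asks for a complete list, and permission to add is not a plan.

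**Conclusion.** The point holds in a limited form. The SAP names only central parameters for its laboratory summaries, and no listed table counts subjects who meet the laboratory criteria of protocol 11.2. What is lost is a systematic count, by arm, of early threshold crossings that were neither reported as adverse events nor still present at a central draw.

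The schedule count (four of five local days, or three of four) comes straight from the documents. The catch rates do not: even onset and durations of one to four days are assumptions, and the documents give no basis for choosing among them. They show that the gap concerns changes of about three days or less, and that it largely closes for longer ones. This is worth correcting as a cheap improvement to the safety comparison; it does not show that a signal was missed.

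**What to change.** 1. Add one table by arm on the safety population: number and percentage of subjects with any post-dose creatinine above 2.0 mg/dL, and with each and all of Hy's law items a to c. Use all local and central values, scheduled and unscheduled. Mark item d as needing medical review.
2. Add by-day summaries by arm of local creatinine, AST, ALT, ALP and total bilirubin for Days 1–5, and include the local values in the laboratory listing, which should be added to SAP 14.1.
3. Reconcile the start day of the local tests between footnote k of protocol 9.1 and footnote k of SAP 3.2.
4. Before any by-arm table is read, reconcile the group labels in SAP section 13, which pair the high-dose group with L and the low-dose group with H.

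The cost is a small amount of programming on data already in the case report form. Site reference ranges are needed for the multiples of the upper limit of normal, and the documents do not show that these are collected. The creatinine count needs none and can go ahead regardless.

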7.3.3 Vital Signs

All vital sign data will be listed.

Vital signs (systolic blood pressure, diastolic blood pressure, pulse rate, body temperature) values and changes from baseline will be summarized descriptively by analysis visit.

7.3.4 12-lead ECG

All 12-lead ECG (heart rate, RR, PR, QRS, QT, QTcF, overall evaluation) parameters and findings will be listed.

12-lead ECG parameter values and changes from baseline will be summarized descriptively by analysis visit.

For ECGs, number and percentage of subjects meeting the criteria listed below will be presented:

- $QTcF > 500$ msec at timepoint
- $500 \geq QTcF > 480$ msec at time point
- $480 \geq QTcF > 450$ msec at time point
- Change from baseline in $QTcF > 30$ msec
- Change from baseline in $QTcF > 60$ msec

Number of normal or abnormal values will be summarized by analysis visit window.

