The investigator (subinvestigator) will measure all of the following tests at the contract laboratory testing institution on Day4 (before the end of continuous intravenous infusion), Day7, Day10, Day14, Week 3, and at discharge, and record the date of confirmation of test results and the results of confirmation (clinical significance). The test results provided by the contract laboratory testing institution will be retained by the study site and the sponsor.

The test items are as follows.

- Hematology: white blood cell count (WBC), red blood cell count (RBC), hematocrit (Ht),
Hemoglobin (Hb), Platelets (Plt)
- Blood biochemistry: AST (GOT), ALT (GPT), LDH, ALP, γ -GTP,
Total bilirubin (T-Bil), direct bilirubin (D-Bil),
Total cholesterol (T-Chol), triglycerides (TG), total protein (TP),
CK (CPK), Blood urea nitrogen (BUN), Serum creatinine (Cre), eGFR,
Uric acid (UA), Na, K, Cl, albumin, glucose
- Urinalysis (qualitative): Sugar, protein, occult blood

(2) Standard 12 lead ECG

The investigator (subinvestigator) will perform standard 12 lead ECG at baseline and Day4 (before completion of continuous intravenous infusion) to determine whether there are any abnormal findings. The date and time of standard 12 lead ECG, ECG parameters (Heart rate, PR interval, QRS interval, RR interval, QT interval, and QTc interval), and assessment results will be recorded in the CRF. Clinically significant abnormal findings, if determined by the investigator or subinvestigator, should be recorded as adverse events. The investigator will maintain ECG charts as source documents.

(3) Vital signs

The investigator/subinvestigator will measure systolic/diastolic blood pressure, pulse rate, and body temperature (Axillary, oral or tympanic body temperature) before administration, on Day4 (before the end of continuous intravenous infusion), Day7, and Day14, and record the date of measurement and the test results in the case report form. Blood pressure should be measured in the same arm throughout the study period whenever possible. Clinically significant abnormal findings, if determined by the investigator or subinvestigator, should be recorded as adverse events.

(4) Neurological Examination

The Investigator (or Subinvestigator) will perform a neurological examination on the healthy side once from the onset to Day5, and then on Day14, Week 3, at the time of discharge, and 3 months later. The tests that may be

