14.2 Tables

No.	Title of table	Analysis Population/Dataset
14.1 – STUDY		
14.1.1.1	Analysis Populations	All Subjects
14.1.1.2	Subject Dispositions	All Subjects
14.1.2.1	Baseline Demographics	All Subjects
14.1.2.2	Medical History	All subjects
14.1.2.3	Summary of IMP Exposure for Continuous Infusion Dosing Regimen	All subjects
14.1.2.4	Summary of IMP Exposure for Approved dosing regimen	All subjects
14.2 – EFFICACY		
14.2.1.1	Summary of NIHSS (Change from Pre-NIHSS Score ≥ 4)	FAS
14.2.1.2	Summary of NIHSS	FAS
14.2.1.3	Summary of mRS	FAS
14.2.1.4	Summary of BI	FAS
14.2.1.5	Summary of BI(100-95, 90-55, 50)	FAS
14.2.1.6	Summary of FIM	FAS
14.2.1.7	Summary of FIM(moter item, cognitive item)	FAS
14.2.1.8	Summary of Duration of hospitalization	FAS
14.2.1.9	Summary of Start of rehabilitation	FAS
14.3 – SAFETY		
14.3.1.1	Overall Summary of Treatment Emergent Adverse Events	SAF
14.3.1.2	Summary of Treatment Emergent Adverse Events by System Organ Class and Preferred Term	SAF
14.3.1.3	Summary of Adverse Drug Reaction by System Organ Class and Preferred Term	SAF
14.3.2.1	Summary of Hematolog	SAF
14.3.2.2	Summary of Biochemical	SAF
14.3.2.3	Summary of Urianalysis	SAF
14.3.2.4	Shift Table for Hematology	SAF
14.3.2.5	Shift Table for Biochemical	SAF
14.3.2.6	Shift Table for Urianalysis	SAF
14.3.3.1	Summary of Vital Signs	SAF
14.3.4.1	Summary of 12 lead ECG parameters	SAF
14.3.4.2	Number of Subject Meeting QTcF Criteria in 12-lead ECG	SAF
14.3.4.3	Summary of 12-lead ECG - Number of Normal/Abnormal values	SAF
14.4 – [REDACTED]		
14.4.1.1	Summaey of [REDACTED]	All subjects

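### No baseline-to-Day 4 shift table is planned for the ECG normal/abnormal evaluation, so no summary table shows by group how many subjects became newly abnormal on the infusion

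*SAP*

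**What the plan says.** **Collection.** Protocol 9.2.4.1 (2) has the investigator "perform standard 12 lead ECG at baseline and Day4 (before completion of continuous intravenous infusion", in order to judge whether any finding is abnormal. The SAP schedule (Table 1) shows the same two time points and no ECG at discontinuation or later. A finding that the investigator judges clinically significant is to be recorded as an adverse event.

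**Normal/abnormal evaluation.** SAP 7.3.4 says "Number of normal or abnormal values will be summarized by analysis visit window". The matching output in SAP 14.2 is Table 14.3.4.3, "Summary of 12-lead ECG - Number of Normal/Abnormal values". No ECG shift table appears in the list.

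**Other ECG analyses in SAP 7.3.4.** "12-lead ECG parameter values and changes from baseline will be summarized descriptively by analysis visit". Subjects with a QTcF rise above 30 or 60 msec from baseline are counted, as are subjects in three absolute QTcF bands at each time point. "All 12-lead ECG (heart rate, RR, PR, QRS, QT, QTcF, overall evaluation) parameters and findings will be listed" (Listing 16.2.7.2).

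**Laboratory categories.** SAP 7.3.2 says "Shift tables will present the changes in clinically relevant categories from baseline to each analysis visit", delivered as Tables 14.3.2.4 to 14.3.2.6 for hematology, biochemistry and urinalysis.

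**The concern.** With one ECG before treatment and one during the infusion, the natural safety question for a normal/abnormal evaluation is how many subjects in each group were normal before and abnormal on Day 4. Separate counts per visit do not answer it. Subjects who become abnormal are offset by subjects whose pre-dose abnormality is no longer present, and only the net difference can be seen.

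Pre-dose abnormalities are plausible here, because cardioembolic stroke is one of the disease types recorded in Protocol 9.2.1. The documents give no rate.

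Missing Day 4 ECGs add to the difficulty. A subject who stops before the Day 4 ECG window (study days 3 to 4 in SAP Appendix 1) counts at baseline only, and SAP section 6 imputes nothing. The two counts can then describe different sets of people.

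At stake is the readability of one safety table. If the high-dose infusion produced new ECG abnormalities that investigators did not judge clinically significant, no by-group summary of the evaluation would count them.

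**Working it through.** The plan states no figure to reproduce. The check is what two marginal counts can and cannot determine.

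**Inputs from the documents.** Two ECG time points (Protocol 9.2.4.1; SAP Table 1). Counts by visit only (SAP 7.3.4; Table 14.3.4.3). Planned size of the H group and of the control group, 120 each (Protocol 6.1).

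**Inputs assumed.** The proportions abnormal, and 40 subjects per group as an example of a group smaller than planned. The documents give neither. Pairs are taken as complete.

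**Formula.** In a group of n subjects let a be abnormal at baseline, b abnormal on Day 4, and k the number going from normal to abnormal.

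- The newly abnormal come from the n − a subjects normal at baseline, so k ≤ n − a. They are among the b abnormal on Day 4, so k ≤ b.
- The remaining b − k abnormal on Day 4 were already abnormal, so b − k ≤ a, that is, k ≥ b − a.

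Hence max(0, b − a) ≤ k ≤ min(b, n − a).

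| n | a (baseline) | b (Day 4) | max(0, b − a) | min(b, n − a) | newly abnormal, k |
|---|---|---|---|---|---|
| 40 | 12 | 12 | max(0, 0) = 0 | min(12, 28) = 12 | 0 to 12 |
| 40 | 16 | 16 | max(0, 0) = 0 | min(16, 24) = 16 | 0 to 16 |
| 40 | 4 | 12 | max(0, 8) = 8 | min(12, 36) = 12 | 8 to 12 |
| 40 | 12 | 4 | max(0, −8) = 0 | min(4, 28) = 4 | 0 to 4 |
| 120 | 36 | 36 | max(0, 0) = 0 | min(36, 84) = 36 | 0 to 36 |
| 120 | 12 | 36 | max(0, 24) = 24 | min(36, 108) = 36 | 24 to 36 |

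**Reading the table.** The counts fix b − a, which equals newly abnormal minus resolved. They do not fix k. When few subjects are abnormal at baseline the range is narrow (8 to 12 in the third row). When more are abnormal and the two counts are equal, it runs from zero up to the full Day 4 count.

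**Two groups with the same printed result.** Suppose each group has 40 subjects with 12 abnormal at both visits. In one, the same 12 subjects are abnormal throughout (k = 0). In the other, all 12 read normal on Day 4 and 12 others have become abnormal (k = 12). This is the extreme case, but Table 14.3.4.3 would print the same figures for both groups. A baseline-by-Day 4 cross-table would print 0 and 12.

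**Comparison within the SAP.** Laboratory categories get a baseline shift and the ECG category does not; no reason is given. The protocol does not explain the difference either. Protocol 13.3.3 names shift tables only for the neurological examination and urinalysis, so the hematology and biochemistry shifts are already additions made in the SAP.

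**The case against.** The case against the point is substantial, and most of it stands as a limit on its scope.

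- **Most ECG data are compared with baseline.** A reader might infer that ECG results in general are cut off from the subject's own baseline. The documents do not support that. Heart rate, RR, PR, QRS, QT and QTcF are all summarised as changes from baseline, and QTcF rises are counted against two thresholds. Only the overall evaluation and the absolute QTcF bands are reported visit by visit. The bands sit beside the change counts, so cross-tabulating them by baseline band is optional.
- **New abnormalities can be found.** A reader might infer that they cannot be told from pre-existing ones at all. That is too strong. Listing 16.2.7.2 includes the overall evaluation, and SAP section 13 orders listings by treatment, subject and visit, so both evaluations of one subject can be read together within group. What stands is that the reader must build the count by hand. The SAP also lists laboratory data in full and still tabulates their shifts.
- **Adverse events catch what matters clinically.** Clinically significant findings that start or worsen after dosing enter the treatment-emergent tables (SAP 7.3.1). Conversions judged not significant do not.
- **It is not a departure from the protocol.** Correct: Protocol 13.3.3 plans no ECG shift table. This is an analysis choice.
- **Little depends on it.** Recruitment stopped early, SAP section 1 calls the results exploratory, and no stated decision uses this table. That bears on severity, not on what the table can show.

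A reader might also suspect that the reported QTcF is a site value under another correction, because the protocol's recorded items end with "QT interval, and QTc interval" and name no formula. The documents do not say so. QTcF itself names the Fridericia correction, and the QT and RR needed for it are collected. That suspicion forms no part of this point.

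**Conclusion.** The point holds in a narrow form. The overall ECG evaluation is a paired normal/abnormal outcome that SAP 7.3.4 and Table 14.3.4.3 reduce to one count per visit. As a result, no summary table shows by group how many subjects became newly abnormal during the infusion, and conversions not judged clinically significant appear only in the listing.

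The arithmetic rests on assumed counts and complete pairs: 0 to 12 newly abnormal with 12 of 40 at both visits, and 0 to 36 with 36 of 120. The true ambiguity depends on the baseline rate, which the documents do not give, and it shrinks as that rate falls. I take the normal/abnormal count to refer to the overall evaluation, because SAP 7.3.4 sets no normal ranges for the ECG parameters.

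Severity is low. The data are collected and listed, the other ECG summaries use baseline, and no stated conclusion of the study changes.

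**What to change.** Re-lay Table 14.3.4.3 as a shift table by treatment group, with baseline (normal / abnormal) in rows and Day 4 (normal / abnormal / missing) in columns. The row and column totals keep the per-visit counts now planned, and the missing column shows who has no Day 4 ECG. Change the sentence in SAP 7.3.4 to match.

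The cost is one sentence of SAP text and the programming of one table layout. SAP section 6 already defines baseline as the last valid assessment before dosing, and both evaluations are recorded, so no new data and no protocol change are needed.
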